8.4 Data analysis plan

- 8.4.1 For each subject, the difference in score for the PFIQ-7 and PISQ-IR for the current and the study pessary will be calculated.

8.5 Reportable outcomes

- 8.5.1 Average and standard deviation of the PFIQ-7 and PISQ-IR for the current and study pessary will be reported.
- 8.5.2 We will use a two-tailed t-test to test the null hypothesis that the mean difference score between baseline (current pessary) and study pessary on the PFIQ-7 is zero. This test is equivalent to a matched samples t-test. The p-value will be reported.
- 8.5.3 We will use a two-tailed t-test to test the null hypothesis that the mean difference between baseline (current pessary) and study pessary on the PISQ-IR is zero. This test is equivalent to a matched samples t-test. The p-value will be reported.

\* Printed copies are uncontrolled unless otherwise identified \*

Before using this document, consult Grand Avenue to confirm current version before use.

CONFIDENTIAL

## TITLE COLLAPSIBLE PESSARY FEASIBILITY TRIAL STATISTICAL ANALYSIS PLAN

**9.0 ABILITY TO SUPPORT PROLAPSE (SECONDARY)**

- 9.1 Endpoint
  - 9.1.1 Objective assessment of the study pessary's ability to support anterior prolapse compared to current pessary
  - 9.1.2 Objective assessment of the study pessary's ability to support posterior prolapse compared to current pessary
- 9.2 Data collection method
  - 9.2.1 Modified POP-Q points Ba and Bp (measurements of anterior and posterior prolapse) will be measured during physical exam, with the pessary in situ.
- 9.3 Analysis group
  - 9.3.1 At most, for each subject two Ba and two Bp measurements will be collected for each of the current pessary and the study pessary.
  - 9.3.2 Subject's Ba and Bp measurements will be included in the comparative analysis if the subject has at least 1 data point for both the study pessary and their current pessary and did not drop out because of failure to fit.
- 9.4 Data analysis plan
  - 9.4.1 For each subject, average Ba and Bp scores for the current pessary and study pessary will be calculated.
  - 9.4.2 For each subject, a difference (current pessary – study pessary) in Ba and Bp scores will be calculated.
- 9.5 Reportable outcomes
  - 9.5.1 Average and standard deviation of the Ba and Bp with the current and study pessary will be reported.
  - 9.5.2 Mean difference (current pessary – study pessary) in Ba and Bp scores will be reported.
  - 9.5.3 We will use a two-tailed t-test to test the null hypothesis that the mean difference score between baseline (current pessary) and study pessary on the Ba is zero. This test is equivalent to a matched samples t-test. The p-value will be reported.
  - 9.5.4 We will use a two-tailed t-test to test the null hypothesis that the mean difference score between baseline (current pessary) and study pessary on the Bp is zero. This test is equivalent to a matched samples t-test. The p-value will be reported.
  - 9.5.5 Due to intra- and inter- observer variation in the measurements for Ba and Bp, a difference  $> 1.5$  cm is considered meaningful change. This analysis will be a one-sample, equivalence design. We will use 2, one-sided t-tests, to test the composite null hypothesis that the mean difference score between baseline (current pessary) and study pessary on the Ba measurement is less than or equal to  $-1.5$  cm and greater than or equal to  $1.5$  cm. The p-value will be reported.
  - 9.5.6 We will use 2, one-sided t-tests, to test the composite null hypothesis that the mean difference score between baseline (current pessary) and study pessary on the Bp measurement is less than or equal to  $-1.5$  cm and greater than or equal to  $1.5$  cm. The p-value will be reported.

\* Printed copies are uncontrolled unless otherwise identified \*

Before using this document, consult Grand Avenue to confirm current version before use.

CONFIDENTIAL

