## TITLE COLLAPSIBLE PESSARY FEASIBILITY TRIAL STATISTICAL ANALYSIS PLAN

**12.0 SUCCESS & EASE OF FITTING (SECONDARY)**

- 12.1 Endpoint
  - 12.1.1 Proportion of subjects successfully fit with the study pessary
  - 12.1.2 Number of study pessaries required to fit
- 12.2 Data collection method
  - 12.2.1 If subject is unable to be fit with a study pessary it will be recorded
  - 12.2.2 Size of each study pessary tried will be recorded
- 12.3 Analysis group
  - 12.3.1 All subjects who complete the study will be considered successfully fit.
  - 12.3.2 For those who do not complete the trial, if the study team indicates that the reason for withdrawal is failure to fit or failure to retain, the subject will be considered failed to fit. If the study team indicates that the reason for withdrawal is discomfort with the study pessary and multiple sizes of study pessary have been tried, the subject may be considered failed to fit. This may be indicated on the data collection form or in data safety monitoring meetings. All other subjects who received the study pessary and were not deemed fit failures will be considered successfully fit.
  - 12.3.3 For subjects who are successfully fit, each size tried will be considered a study pessary required to fit.
- 12.4 Data analysis plan
  - 12.4.1 A count of subjects who were successfully fit will be calculated.
  - 12.4.2 A count of subjects who failed to be fit will be calculated.
  - 12.4.3 A proportion of subjects successfully fit to total subjects (successfully fit + failed to fit) will be calculated.
  - 12.4.4 A count of total pessaries used will be calculated for each subject who completed.
  - 12.4.5 An average of number of pessaries required to successfully fit will be calculated.
- 12.5 Reportable outcomes
  - 12.5.1 The proportion of subjects successfully fit will be reported.
  - 12.5.2 The average pessaries required to fit will be reported.

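### SAP 9.3.2 discards observed paired Ba/Bp data from women withdrawn as fit failures: probably few women, but an outcome-dependent exclusion that should not define the only support analysis

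*SAP*

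**What the plan says.** The endpoint in SAP 9.1 is "Objective assessment of the study pessary's ability to support anterior prolapse compared to current pessary", with a matching endpoint for posterior prolapse. It is not described as conditional on the pessary having been retained.

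SAP 9.3.1 allows up to two readings per pessary: "At most, for each subject two Ba and two Bp measurements will be collected for each of the current pessary and the study pessary". They are averaged within woman, and a current-minus-study difference is taken (9.4). SAP 9.3.2 then sets two joint conditions: at least one data point on the study pessary and one on "their current pessary and did not drop out because of failure to fit".

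The differences are tested against zero (9.5.3, 9.5.4) and for equivalence within 1.5 cm (9.5.5, 9.5.6). In 9.5.5 a difference above 1.5 cm "is considered meaningful change. This analysis will be a one-sample, equivalence design".

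Section 9 does not define failure to fit. The only working definition is in 12.3.2. Among non-completers, if "the reason for withdrawal is failure to fit or failure to retain, the subject will be considered failed to fit". Where the reason is discomfort and "multiple sizes of study pessary have been tried, the subject may be considered failed to fit", the label is a matter of judgement, and it may be recorded on the data form or arise in the safety monitoring meetings. Under 12.3.1, completers count as successfully fit.

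**The concern.** The two conditions in 9.3.2 do different work. Requiring data on both pessaries deals with missing measurements. Once it is applied, the only women left for the failure-to-fit clause to act on are those with usable paired data. The clause therefore has no missing-data function; it removes observed outcomes.

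The removal depends on something that happens after the study pessary is placed and that is plausibly related to the outcome. A pessary that is not retained may also have been supporting poorly while in place. Part of the label is discretionary, in a trial where subject and investigator both know the device. At stake is whether the reported mean difference, and both tests on it, describe all women measured on both pessaries or only those in whom the study pessary did not fail on fit. Section 9 does not label the restricted set as per protocol and offers no analysis that includes the women removed.

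**Working it through.** The documents give no sample size, power or standard deviation for Ba/Bp, so there is no stated figure to reproduce. The check has three parts.

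**1. Who can be removed?** The visit schedule is in Protocol section 6.0.
- Visits 0 and 1: support is measured with the current pessary in situ. No in-situ support measurement of the study pessary is described at Visit 1.
- Visit 2: if held in person, support with the study pessary in situ is measured. The visit may be omitted.
- Visit 3: the study pessary is measured, but women who complete the study are fit successes by definition (SAP 12.3.1).
- Additional visits: no Ba/Bp measurement is specified.

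So the clause reaches women measured at an in-person Visit 2 and then withdrawn as fit failures. Protocol section 13.0 allows this, because withdrawal for repeated expulsion is not tied to a visit. The endpoint table in Protocol section 4.0 lists Ba/Bp at Weeks 0, 3-5 and 16 and omits Weeks 5-7. However, the two study-pessary readings allowed by SAP 9.3.1 can only come from Visits 2 and 3, so Visit 2 values appear to count.

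**2. How does the SAP treat the same women elsewhere?**
- Pain (11.3.1) and ease (14.3.1): included in the comparison with at least one data point on each pessary; no fit-failure exclusion.
- Satisfaction (10.3.1): women who leave early are kept if they gave both scores.
- PFDI-20: drop-outs after Visit 1 stay in the primary analysis with an assigned score (6.3.1). Excluding fit failures is only a secondary per protocol analysis (6.3.2).

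Only for Ba/Bp is the restricted set the sole set.

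**3. How large could the effect be?** Assumptions: 40 retained women (the planned number of completers, Protocol section 6.0) with mean difference 0, and *k* excluded women each *d* cm worse on the study pessary. Negative differences mean worse support with the study pessary.

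Shift in mean = *k* × *d* / (40 + *k*), in cm:

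| *k* | *d* = 2 | *d* = 3 | *d* = 4 |
|---|---|---|---|
| 1 | 0.05 | 0.07 | 0.10 |
| 2 | 0.10 | 0.14 | 0.19 |
| 3 | 0.14 | 0.21 | 0.28 |
| 5 | 0.22 | 0.33 | 0.44 |

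Smallest: 1 × 2 / 41 = 0.05 cm, and 0.05 / 1.5 = 3% of the margin. Largest: 5 × 4 / 45 = 0.44 cm, and 0.44 / 1.5 = 30%. For 5 women to move the mean from 0 to -1.5 cm, each would need a deficit of 1.5 × 45 / 5 = 13.5 cm.

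The effect on the tests was simulated with 20,000 normal samples per case. Excluded women average -3 cm, and the SD is assumed to be 1.0 to 2.0 cm. Alpha is .05 per one-sided test, taken from 6.5.1 because section 9 states none. Each cell shows none / 2 / 5 excluded women added back.

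| Retained mean | SD | Equivalence declared | Two-tailed t-test shows worse support |
|---|---|---|---|
| 0 | 1.0 | 100% / 100% / 100% | 2.5% / 7.7% / 29.5% |
| 0 | 1.5 | 100% / 100% / 99.9% | 2.5% / 6.2% / 19.0% |
| 0 | 2.0 | 99.7% / 99.6% / 97.7% | about 2.5% / 5.6% / 14.1% |
| -0.75 | 1.0 | 99.9% / 98.7% / 89.9% | 99.6% / 99.9% / 100% |
| -0.75 | 1.5 | 93% / 84% / 65% | 87% / 94% / 99% |
| -0.75 | 2.0 | 75% / 64% / 46% | 64% / 76% / 89% |

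In the last three rows the mean moves from -0.75 to (40 × -0.75 + 2 × -3) / 42 = -0.86 cm with 2 women, and to (40 × -0.75 + 5 × -3) / 45 = -1.00 cm with 5.

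**The case against.** A reader might infer that the plan strips the device's failures out of its own support endpoint and so biases the result in its favour. The documents do not support that, for four reasons.

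- **Reach.** Many fit failures will have no in-situ study-pessary reading, since an expelled pessary cannot be measured. They drop out under the data requirement, and deleting the clause would not bring them back. Women who leave for other device-related reasons with paired data are already kept.
- **Direction.** Ba/Bp is read with the pessary in place. Expulsion and discomfort are different failures, and a woman withdrawn for discomfort may have had adequate measured support.
- **Size.** Planned attrition is about 50 - 40 = 10 women from all causes, including withdrawals during washout. Scenarios with 8 or more measured fit failures would use up most of it.
- **Visibility.** Fit failures are counted in the fit proportion (12.4.2, 12.4.3), belong to the safety group (7.3.1), and stay in the primary PFDI-20 analysis if they completed Visit 1 (6.3.1).

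It can also be argued that support among women who could be fitted is a reasonable question. Section 9 is secondary, in a feasibility study, and has reportable outcomes rather than a success criterion.

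All of this stands as a limit on the point, but none of it justifies the clause. If it removes nobody, deleting it costs nothing; if it removes somebody, it discards collected outcome data on an outcome-related label. Nor does the optional Visit 2 settle the matter: it may be skipped when the woman is doing well, so those seen in person are more likely to be those with problems. If support among fitted women is the intended question, section 9 should say so.

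**Conclusion.** The point holds as one about the analysis set. The failure-to-fit clause in 9.3.2 can only remove women with observed paired support data, it does so on a post-treatment and partly discretionary label, and it is out of line with the SAP's other paired comparisons and with its own treatment of the PFDI-20.

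The number affected is probably small. A bias in favour of the study pessary is conditional on poorer measured support in these women, which is plausible but not shown. For 1 to 5 women the illustrative shift stays well inside the margin. With a retained mean near 0 the equivalence conclusion would rarely change; it becomes sensitive if the retained mean is already negative. The test against zero is the more exposed result at a retained mean of 0. The number of women, their deficit, the SD, the retained mean and the section 9 alpha are all assumptions. The reading also depends on Visit 2 values being used; if they were not, the clause would remove almost nobody.

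**What to change.** - In SAP 9.3.2, delete the final condition on drop-out because of failure to fit. The main Ba/Bp analysis then includes every woman with at least one in-situ measurement on each pessary.
- Keep the present restricted set as a sensitivity analysis, labelled per protocol, as 6.3.2 does for the PFDI-20.
- Beside the result, report how many fit failures had in-situ study-pessary data and how many did not, so that the reader can see what neither set can recover.

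The cost is a small change of SAP wording and one extra run of the same tests. No new data are needed. The main estimate may become slightly less favourable to the study pessary.

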## TITLE COLLAPSIBLE PESSARY FEASIBILITY TRIAL STATISTICAL ANALYSIS PLAN

**10.0 GLOBAL SATISFACTION (SECONDARY)**

- 10.1 Endpoint
  - 10.1.1 Global assessment of study pessary satisfaction compared to current pessary
  - 10.1.2 Global assessment of study pessary satisfaction
- 10.2 Data collection method
  - 10.2.1 Satisfaction will be assessed using a Visual Analog Scale (VAS) with a 10 cm linear continuum in which 0 represents no satisfaction and 10 represents complete satisfaction.
- 10.3 Analysis group
  - 10.3.1 Global satisfaction is recorded at visit 1 for the current pessary and visit 3 for the study pessary, so only subjects who complete data collections forms through visit 3, or provide a score for both the current and study pessary before exiting the study, will be included in the analysis.
- 10.4 Data analysis plan
  - 10.4.1 For each subject, a difference (current pessary – study pessary) in satisfaction scores will be calculated.
- 10.5 Reportable outcomes
  - 10.5.1 Average and standard deviation of the global satisfaction of current and study pessary will be reported.
  - 10.5.2 Mean difference (current pessary – study pessary) in satisfaction scores will be reported.
  - 10.5.3 We will use a two-tailed t-test to test the null hypothesis that the mean difference score between baseline (current pessary) and study pessary for global satisfaction is zero. This test is equivalent to a matched samples t-test. The p-value will be reported.
  - 10.5.4 Cundiff et al. dichotomized VAS scores for pessary satisfaction into high satisfaction (greater than or equal to 80 mm) and low satisfaction (less than 80 mm). For this study, we similarly deemed a VAS of 80 mm would indicate high satisfaction. We will use a one-sided t-test to test the null hypothesis that the mean global satisfaction score for the study pessary is less than 80 mm. The p-value will be reported.

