6.0 Procedures Involved

Methods

This is a non-randomized prospective trial. Treatment intervention will be non-blinded to the subject and the investigator. Subjects will serve as their own controls and enter the treatment phase of the study after a 1-month washout period of using their current pessary. Subjects will be recruited for this study from panels of patients in clinical practices specializing in Female Pelvic Medicine and Reconstructive Surgery (FPMRS). Inclusion will be based on pre-defined criteria outlined in "10.0 Inclusion and Exclusion Criteria."

The primary outcome measure will be the change in the scores of the Pelvic Floor Distress Inventory-20 (PFDI-20), administered first during the washout period while still using their current pessary and then at the conclusion of the treatment phase with the study pessary. The PFDI-20 is a validated health-related quality of life instrument to assess the *presence and bother of symptoms* in women with pelvic floor dysfunction. For women with relatively mild pelvic floor symptoms, a minimal important change (MIC) of between 13.5 and 18.3 points in the PFDI-20 score can be considered clinically relevant. At least fifty subjects will be enrolled, expecting that after drop-out and attrition at least 40 subjects will have completed the study. This provides power of .80 for a MIC equivalence limit of 17 points on the PFDI-20 scale.

There will not be discrimination based on race or ethnicity. It is anticipated that most participants will be post-menopausal as this reflects the demographic of women who suffer from this disorder.

The study will take place over 4 visits (Visit 0, Visit 1, Visit 2, and Visit 3).

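### The 80 mm satisfaction cut-off classifies individual women, but SAP 10.5.4 applies it only to a group mean; separately, the analysis set has no rule for women who leave without a score

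*SAP*

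**What the plan says.** SAP 10.5.4 explains that a cited crossover trial of ring and Gellhorn pessaries "dichotomized VAS scores for pessary satisfaction into high satisfaction" (at least 80 mm) and low satisfaction (below 80 mm). For this trial it adds: "we similarly deemed a VAS of 80 mm would indicate high satisfaction". The planned test is a one-sided t-test of the null that the "mean global satisfaction score for the study pessary is less than 80 mm". The rest of SAP 10.5 plans means, standard deviations, a mean difference and a paired test, but no count or proportion of women at or above 80 mm.

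SAP 10.3.1 defines one analysis group for both satisfaction endpoints, the comparative 10.1.1 and the non-comparative 10.1.2: "only subjects who complete data collections forms through visit 3, or provide a score for both the current and study pessary before exiting the study". No value is assigned to a woman without a score.

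Section 10.5 is headed as reportable outcomes. It says "The p-value will be reported" and gives neither an alpha nor a success criterion.

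The protocol (4.0 endpoint table and 6.0, Visit 3) schedules study-pessary satisfaction only at Visit 3, the end of treatment. On numbers, Protocol 6.0 enrols at least fifty, "expecting that after drop-out and attrition at least 40 subjects will have completed the study".

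**The concern.** There are two faults, and neither causes the other.

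**The summary does not match the cut-off.** A threshold that says whether one woman is highly satisfied does not say what a group mean of 80 mm signifies. A mean above 80 mm can coexist with many women below it, and a few very low scores can pull the mean under 80 mm when most women are above it. As planned, the report would never state how many women were highly satisfied, which is what the cited definition measures.

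**Entry to the analysis depends on staying, or on happening to give a score.** Protocol 13.0 lists fit failure, repeated expulsion, discomfort and adverse reaction among the reasons for withdrawal. Each is plausibly linked to low satisfaction, and a woman who leaves for one of them has no scheduled satisfaction assessment. The SAP deals with dropout for PFDI-20, where 6.3.1 keeps women who drop out after Visit 1 and assigns them an unfavourable value. Section 10 has no counterpart.

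At stake is a secondary result that reads as high satisfaction with the device but describes only women who supplied scores.

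**Working it through.** **Inputs.** From the documents: threshold 80 mm, one-sided one-sample t-test, at least 50 enrolled and at least 40 completing. The documents give no satisfaction mean, SD, dropout score or alpha. Those below are assumptions, with 0.05 one-sided used as the reference line. The plan contains no design calculation for satisfaction to reproduce; the stated power concerns PFDI-20 only.

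**1. Mean against proportion (40 scores, invented to show the mismatch).** t = (mean − 80)/(SD/√40), 39 df.

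| Scores | Mean | SD | t | One-sided p | At or above 80 mm |
|---|---|---|---|---|---|
| 22 at 100, 18 at 70 | 86.5 | 15.1 | 2.72 | 0.005 | 22/40 = 55% |
| 32 at 92, 8 at 20 | 77.6 | 29.2 | −0.52 | 0.70 | 32/40 = 80% |

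The second set has far more highly satisfied women and the worse p-value. The mismatch can run for or against the device.

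**2. Sensitivity to unscored dropouts.** Suppose 40 women with scores have mean 85 and SD 18. Then t = 5/(18/√40) = 1.76 and p = 0.043.

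Add one woman at score d. The mean becomes (40×85 + d)/41, and the sum of squares becomes 39×18² + (40/41)(85 − d)².

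| d (mm) | Mean | SD | t (40 df) | p |
|---|---|---|---|---|
| 20 | 83.4 | 20.5 | 1.07 | 0.15 |
| 40 | 83.9 | 19.1 | 1.31 | 0.10 |
| 60 | 84.4 | 18.2 | 1.55 | 0.07 |

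The starting p-value is borderline, and part of the shift comes from the larger SD.

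With k women at d, the mean is (40×85 + kd)/(40 + k). It falls below 80 when k > 200/(80 − d).
- d = 20: k > 3.3, so four women suffice (mean 79.1).
- d = 40: five women give exactly 80, and six give 79.1.
- d = 60: ten women bring it only to 80.

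**3. How often would this mislead?** Simulation of 50 women with 10 lost: normal scores truncated to 0–100, 3,000 runs per cell. Moderate loss means that the chance of dropping out rises as satisfaction falls. The entries are the share of runs with p < 0.05.

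| True mean, all 50 (SD before truncation) | Random loss | Moderate | Ten lowest lost |
|---|---|---|---|
| 79.4 (15) | 2.8% | 34% | 80% |
| 74.0 (20) | 0% | 1.3% | 15% |
| 69.4 (20) | 0% | 0% | 0.4% |

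At a true mean of 79.4, if half of the dropouts give an exit score, 34% and 80% fall to 11% and 23%. If all do, they fall to 2–3%.

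**4. Effect of the denominator.** If 28 of 40 scored women reach 80 mm, that is 70% (exact 95% CI 53–83%). With six further Visit 1 completers unscored, 28/46 = 61% (45–75%). With ten, 28/50 = 56% (41–70%). Ten is an upper-end case, since it puts the whole gap between 50 enrolled and 40 completing after Visit 1.

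**The case against.** A reader might infer that survivor bias can turn a poor result into a declared success. The documents do not support that. Section 10 defines no success for satisfaction; only the two primary endpoints have success criteria (SAP 6.5 and 7.5). The simulation also shows that a true mean well below 80 mm is rarely hidden.

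A reader might also infer that missing scores come mainly from dissatisfied women, or that 50 is the number given the device. Protocol 13.0 lists six reasons without frequencies. Three concern the study pessary; the others are an excluding condition, trouble with the current pessary during washout, and withdrawal by the woman herself. Fifty is the enrolment figure at Visit 0, so some of the expected losses may never meet the device.

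Nor is the analysis confined to women who stayed. SAP 10.3.1 admits women who "or provide a score for both the current and study pessary before exiting the study". The Data Collection Form listed in SAP 3.0 is not among the documents reviewed, so it may prompt for an exit score.

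Finally, losses are partly visible elsewhere: SAP 12 reports fit and retention failures, adverse events cover all Visit 0 completers, and PFDI-20 keeps dropouts.

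These points limit the size of the problem. They do not supply a proportion at or above 80 mm or a rule for missing scores, and the exit route helps only to the extent that scores are actually collected.

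**Conclusion.** Both faults stand, as improvements the sponsor should make rather than threats to the primary conclusion. The mismatch between an individual cut-off and a group mean follows directly from the wording of SAP 10.5.4 and needs no assumption about dropout. It can mislead in either direction.

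The selection fault is conditional. It favours the device if withdrawals are related to low satisfaction and few leavers give a score. That is plausible from Protocol 13.0 but not documented. Its consequence is an over-favourable p-value on a secondary outcome, concentrated where the true mean is just under 80 mm: 34% of simulated trials under moderate satisfaction-related loss at a true mean of 79.4, against 1.3% at 74.0. These rates assume ten unscored losses after fitting, which is at the high end of what the protocol expects.

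**What to change.** 1. Add to SAP 10.5.4 the proportion of women with a study-pessary VAS of at least 80 mm, with an exact 95% confidence interval. Use all women who completed Visit 1 as the denominator, so that those in whom fitting was attempted and failed are included. Count women without a study-pessary score as not highly satisfied. The population matches the one already used for PFDI-20 in 6.3.1.
2. Add a sensitivity analysis that sets aside withdrawals unrelated to the device.
3. Keep the mean test, labelled as applying to women with scores.
4. Collect the satisfaction VAS at any withdrawal visit after Visit 1.
5. For the non-comparative endpoint 10.1.2, do not require a current-pessary score. SAP 11.3.1 and 14.3.1 already define separate non-comparative groups.

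The cost is SAP wording and one VAS at withdrawal. The reported figure will probably be less favourable, and some women who leave for unrelated reasons will be counted as not highly satisfied; the sensitivity analysis shows how much that matters.
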